11.10.7 Confirmation Measurement

Confirmation of CR and PR is required and must occur no fewer than 4 weeks after initial documentation of CR or PR. If CR is pending confirmation and is designated at an assessment followed by 1 or more NE assessments, and/or PR assessments such that the Target Lesion Response is CR and the Non-Target Lesion Response is NE, CR may be confirmed thereafter if Non-Target Lesion Response returns to CR. Similarly, if a PR is pending confirmation and is designated at an assessment followed by 1 or more NE and/or SD assessments, PR may be confirmed thereafter. Subsequent Target Lesion Responses following a CR are limited to CR, PD, or NE; PD for target lymph nodes is met only if any lymph node target lesion reaches a short axis measurement of ≥ 15 mm.

11.11 Appendix 11. Specific Guidance for Cytokine Release Syndrome, Immune-effector Cell-associated Neurologic Syndrome, and Tumor Lysis Syndrome**11.11.1 Specific Guidance for Cytokine Release Syndrome**

Cytokine release syndrome (CRS) is defined as a supraphysiologic response following any immune therapy that results in the activation or engagement of endogenous or infused T cells and/or other immune effector cells. Symptoms can be progressive, must include fever at the onset, and may include hypotension, capillary leak (hypoxia) and end organ dysfunction.

Clinical signs and symptoms of CRS are non-specific and may include a combination of the following:

- constitutional: fever \pm rigors, malaise, fatigue, anorexia, myalgias, arthralgias, nausea, vomiting, headache
- skin: rash
- gastrointestinal: nausea, vomiting, diarrhea
- respiratory: tachypnea, hypoxemia
- cardiovascular: tachycardia, widened pulse pressure, hypotension, increased cardiac output (early), potentially diminished cardiac output (late)
- coagulation: elevated D-dimer, hypofibrinogenemia \pm bleeding
- renal: azotemia
- hepatic: transaminitis, hyperbilirubinemia

The symptoms associated with the CRS event do not meet the definition of an adverse event as defined in Section 11.4. Therefore, the CRS associated event (ie, CRS, cytokine storm) should be documented on the Events electronic case report form (eCRF) as the diagnosis. However, since it is important to document all symptoms related to a CRS event, a CRS Symptoms eCRF will also be available to record the symptoms associated with each CRS event.

If the severity of a CRS event changes from the date of onset to the date of resolution, record a single event for each increased level of severity on the Events eCRF and fill out an associated CRS Symptoms eCRF. If the symptoms worsen enough to impact the overall CRS grade, it is important to remember to record a new CRS event on the Events eCRF with the appropriate grade.

Temperature may normalize within a few hours of treatment, whereas the other components of CRS take longer to resolve. Once such therapies are used, the patient is considered to still have CRS, even in the absence of fever, until all signs and symptoms

leading to the diagnosis of CRS have resolved. Likewise, CRS can be downgraded in an afebrile patient treated with anticytokine therapy as their hemodynamic status and/or hypoxia improves. Typically, a patient with severe CRS in whom fever, oxygen, and pressor requirements have resolved may be assumed to have resolved CRS unless there are alternative causes for the fever, hypoxia, and/or hypotension.

Refer to [Table 6-2](#) for details regarding CRS grading and management. Refer to the regional prescribing information or institutional guidelines (if not addressed in prescribing information) for additional information regarding CRS/immune effector cell-associated neurotoxicity syndrome (ICANS) rescue therapy.

11.11.2 Specific Guidance for Immune-effector Cell-associated Neurologic Syndrome

For this trial, ICANS will be using the criteria referenced in the publication by Lee et al, 2019. While the grading system has been developed in large part from chimeric antigen receptor T cells (CAR-T) therapies, symptoms of ICANS may be shared among immune effector cell-associated therapies such as bispecific T cell engager (BiTE) molecules. Although there may be a wide range of symptoms associated with ICANS, subjects may have a stereotypic course of a specific set of symptoms. The earliest manifestations of ICANS are tremor, dysgraphia, mild difficulty with expressive speech (especially in naming objects), impaired attention, apraxia, and mild lethargy.

Immune effector cell-associated neurologic syndrome grade is determined by the most severe event (eg, depressed level of consciousness, seizure, motor findings, raised intracranial pressure [ICP]/cerebral edema) not attributable to any other cause. Refer to the immune effector cell-associated encephalopathy (ICE) score below for grading of ICANS.

Immune Effector Cell-associated Encephalopathy (ICE) Assessment Tool

The ICE tool was designed to provide objectivity for the grading of multiple overlapping encephalopathy terms. The tool includes an element for assessing the receptive aphasia seen in these subjects. The total score that after assessing the following questions will be used as an input in the determination of the ICANS grade.

- Orientation: Orientation to year, month, city, hospital: 4 points
- Naming: ability to name 3 objects (eg, point to clock, pen, button): 3 points
- Following commands: ability to follow simple commands (eg, "Show me 2 fingers" or "Close your eyes and stick out your tongue"): 1 point

- Writing: ability to write a standard sentence (eg, “Our national bird is the bald eagle”): 1 point
- Attention: ability to count backwards from 100 by 10: 1 point

ICE Scoring

- 7-9, grade 1
- 3-6, grade 2
- 0-2, grade 3
- 0 due to subject unarousable and unable to perform ICE
- Assessment, grade 4

Table 11-7. ASBMT Immune Effector Cell-associated Neurotoxicity Syndrome (ICANS) Consensus Grading for Adults

Neurotoxicity Domain ^a	Grade 1	Grade 2	Grade 3	Grade 4
ICE score ^b	7-9	3-6	0-2	0 (subject is unarousable and unable to perform ICE)
Depression level of consciousness ^c	Awakens spontaneously	Awakens to voice	Awakens only to tactile stimulus	Subject is unarousable or requires vigorous or repetitive tactile stimuli to arouse. Stupor or coma
Seizure	N/A	N/A	Any clinical seizure focal or generalized that resolves rapidly or nonconvulsive seizures on EEG that resolve with intervention	Life-threatening prolonged seizure (> 5 min); or repetitive clinical or electrical seizures without return to baseline in between
Motor findings ^d	N/A	N/A	N/A	Deep focal motor weakness such as hemiparesis or paraparesis
Elevated ICP/cerebral edema	N/A	N/A	Focal/local edema on neuroimaging ^e	Diffuse cerebral edema on neuroimaging; Decerebrate or decorticate posturing; or Cranial nerve VI palsy; or Papilledema; or Cushing's triad

ASBMT = American Society for Blood and Marrow Transplantation; CTCAE = Common Terminology Criteria for Adverse Events; EEG = electroencephalogram; ICANS = immune effector cell-associated neurologic syndrome; ICE = immune effector cell-associated encephalopathy; ICP = intracranial pressure; N/A = not applicable.

^a Other signs and symptoms such as headache, tremor, myoclonus, asterixis, and hallucinations may occur and could be attributable to immune effector-cell engaging therapies. Although they are not included in this grading scale, careful attention and directed therapy may be warranted.

^b A subject with an ICE score of 0 may be classified as grade 3 ICANS if awake with global aphasia, but a subject with an ICE score of 0 may be classified as grade 4 ICANS if unarousable.

^c Depressed level of consciousness should be attributable to no other cause (eg, no sedating medication).

^d Tremors and myoclonus associated with immune effector cell therapies may be graded according to CTCAE v5.0, but they do not influence ICANS grading.

^e Intracranial haemorrhage with or without associated edema is not considered a neurotoxicity feature and is excluded from ICANS grading. It may be graded according to CTCAE v5.0.

Source: Lee et al, 2019

Assessment and Supportive Care Recommendations (all grades)

While management and treatment of ICANS has been developed mainly for patients treated with CAR-T therapies, the principles and therapies for ICANS management may be adapted to patients treated with BiTE molecules. Please refer to [Table 6-2](#) for guidance on management based on the Immune Effector Cell Therapy Toxicity Assessment and Management (also known as CARTOX) for support in clinical decision making (<https://www.mdanderson.org/documents/for-physicians/algorithms/clinical-management/clin-management-cytokine-release-web-algorithm.pdf>).

Refer to the regional prescribing information or institutional guidelines (if not addressed in prescribing information) for additional information regarding SOC therapy.

11.11.3 Tumor Lysis Syndrome

Common Terminology Criteria for Adverse Events (CTCAE) version 5.0 classifies tumor lysis syndrome (TLS) in grade 3 (present), grade 4 (life threatening consequences; urgent intervention indicated) and grade 5 (death). Cairo and Bishop developed a system for defining and grading TLS based on Hande-Garrow classification of laboratory or clinical TLS (Coiffier et al, 2008). In this trial, the Cairo-Bishop classification will be used to define presence of TLS, ie, presence of laboratory TLS (see [Table 11-9](#)) and clinical TLS. Final event grade will be assigned according to CTCAE version 5.0.

Based on the Cairo and Bishop system, laboratory TLS is defined as any 2 or more abnormal serum values present within 3 days before or 7 days after initiation of treatment in the setting of adequate hydration (with or without alkalinization) and use of a hypouricemic agent ([Table 11-9](#)).

Table 11-8. Cairo-Bishop Definition of Laboratory Tumor Lysis Syndrome

Element	Value	Change from baseline
Uric acid	$\geq 476 \mu\text{mol/L}$ or 8 mg/dL	25% increase
Potassium	$\geq 6.0 \text{ mmol/L}$ or 6 mg/L	25% increase
Phosphorus	$\geq 2.1 \text{ mmol/L}$ for children or $\geq 1.45 \text{ mol/L}$ for adults	25% increase
Calcium	$\leq 1.75 \text{ mmol/L}$	25% decrease

Note: Two or more laboratory changes within 3 days before or 7 days after cytotoxic therapy will constitute laboratory tumor lysis syndrome.

Clinical TLS requires the presence of laboratory TLS in addition to 1 or more of the following significant complications: renal insufficiency, cardiac arrhythmias/sudden death, and seizures.

Approval Signatures

Document Name: Protocol Amendment tarlatamab 20210004 4

Document Description: Tarlatamab 20210004 Protocol Amendment 4

Document Number: CLIN-000318238

Approval Date: 19 Jul 2024

Type of Study Protocol: Amendment

Protocol Amendment No.: 4

Document Approvals

Reason for Signing: Management	Name: [REDACTED] Date of Signature: 19-Jul-2024 13:04:36 GMT+0000
--------------------------------	----------------------------------------------------------------------

Summary of Protocol Changes

Protocol Amendment 4

19 July 2024

This protocol was mainly amended due to the evolving data and the availability of pooled population-pharmacokinetics (PK) analysis for tarlatamab to inform and update half-life. The contraception and lactation washout period for tarlatamab was adjusted to align with the Food and Drug Administration (FDA)'s recommended language in the U.S Prescribing Information (USPI). The new duration was set to 5 half-lives, equivalent to 2 months (60 days), after the last dose of tarlatamab for both male and female participants.

Changes including, but not limited to the following were incorporated into the protocol:

- Updated language for subjects with no exposure to prior anti-programmed cell death ligand 1 (PD-[L]1) to include the classification for non-use.
- Added language to specify that ad hoc vital status (survival status) collection may be required to support key study analysis.
- Updated the safety follow-up (SFU) period from 42 (+5) days to 60 (+5) days.
- Clarified the time points for collecting PK and antibody samples.
- Clarified that New York Heart Association (NYHA) assessments collection for screening is only to be performed for subjects with a known history of congestive heart failure to verify exclusion 207.
- Specified that serious adverse events suspected to be related to investigational product that the investigator becomes aware of will be reported to Amgen during the long-term follow-up (LTFU) phase. Language was added to specify that after end of study serious adverse events suspected to be related to investigational product will be reported to Amgen.
- Clarified collection timepoints by adding a window of 7 days in every 6-week (Q6W) visit to allow collection of the [REDACTED] on the same visit.
- Updated the radiological imaging and tumor assessment period to 7 days (previously: 3 days).
- Updated the timeframe for using contraception following the last dose of tarlatamab throughout the protocol, which has now been extended to 60 days for female subjects (previously: 72 days) and 60 days for male subjects and their female partners (previously: 132 days).
- Updated monitoring guidance to include details for Cycle 2+.
- Updated the non-Amgen investigational product information to remove details of strengths and formulation.
- Revised the language for live and live-attenuated vaccines to depict that they are prohibited for a further 60 days after last dose (previously: 42 days).
- Revised the language regarding treatment; post progression to clarify this is permitted for the standard of care arm as well and removed the requirement for radiation therapy.
- Clarified the action required for step-dose rechallenge after tarlatamab delay.
- Revised the language for discontinuation of study treatment to clarify that at minimal vital status (survival status) should be collected, through as an example, direct or family

member contact or family members contact or through the attending physician or medical records, public registries, and public records, subject to local laws and regulations.

- Revised the language for subject discontinuation/withdrawal from the study to clarify that the subject is not considered to have ended the study until there is no means to continue collection of vital status (survival status).
- Clarified the actions to be taken if a subject failed to return to the clinic for a required study visit.
- Updated end of treatment and SFU language to clarify that a subject at minimum should be followed via telephone, clinic visit, or chart review to assess for survival and/or the commencement of subsequent cancer therapy.
- Added information about hypersensitivity reactions (signs, symptoms, and management) based on the latest available data.
- Aligned the adverse event grading scale to be used for Cytokine release syndrome and immune effector cell-associated neurologic syndrome (ICANS).
- Provided examples of local regulatory requirements for reporting suspected unexpected serious adverse reactions (SUSARs).
- Section updated to depict that the patient-reported outcome (PRO) analysis set based on the intent-to-treat (ITT) population and not the PRO analysis set, to avoid potential bias when making direct comparisons between treatment arms, per regulatory health authority recommendations.
- Updated hepatotoxicity language per guidance to capture the new stopping rules and flowchart to align with cited FDA guidance. Updated language.
- General editorial changes, including administrative, abbreviations, typographical, and formatting corrections were made throughout the protocol for clarification.

Changes From Protocol Amendment 3 to Superseding Protocol Amendment 3:

On 14 December 2023, Protocol Amendment 3 was superseded to add a collection of Tumor Tissue (at screening and end of treatment) to the Standard of Care Schedule of Activities.

- To highlight that the rationale for the update to the language in Section on Sample Size Determination, and Overall Survival was to remove one Interim analysis.

This protocol was amended to:

- Update the safety monitoring guidelines to ensure subject safety when receiving tarlatamab, in alignment with data presented to and in agreement with regulatory agencies.
- Update the collection of patient reported outcomes to include an indication of taste changes, in agreement with regulatory agencies.
- Update the study rationale, dose justification, and benefit/risk profile based on the latest
- data regarding antitumor activity in subjects with extensive stage small cell lung cancer (ES-SCLC) in a phase 2 and phase 1 study.
- Remove the “Sucrose mediated renal impairment” potential risk of Tarlatamab based on updated data (Global).
- Update the Schedule of Activities to ensure assessment timing and collection is performed as intended to achieve the goals of the study.
- Update the eligibility criteria for stricter guidance on hepatitis B and C exclusion criteria.
- Update the eligibility criteria on brain metastasis exclusion criteria.
- Update the eligibility criteria with clarification on “mixed histology” exclusion criteria.
- Update in the recommendation guidelines for the management of cytokine release syndrome (CRS) to include the consideration for administration of dexamethasone in grade 1 and 2 CRS.
- To update Dose modification guidelines for ICANS and related neurological events and seizures in alignment with Immune Effector Cell Toxicity Assessment and Management (also known as CARTOX) guidelines.
- To remove language that disease progression of SCLC and death due to disease progression are not considered and reported as adverse events or serious adverse events as this does not apply to studies that are ongoing.
- To update the language in Regulatory Reporting Requirements for Safety Information to incorporate language in alignment across Amgen protocols.
- Other administrative, typographical, abbreviation, and formatting changes were made throughout the protocol for consistency and clarification as needed.

This protocol was amended to:

- Update the safety monitoring guidelines to ensure subject safety when receiving tarlatamab, in alignment with data presented to and in agreement with regulatory agencies.
- Update the collection of patient-reported outcomes to include an indication of taste changes, in agreement with regulatory agencies.
- Update the study rationale, dose justification, and benefit/risk profile based on the latest data regarding antitumor activity in subjects with extensive stage small cell lung cancer (ES-SCLC) in a phase 2 (Study 20200491) and phase 1 study (Study 20160323).
- Remove the “Sucrose mediated renal impairment” potential risk of Tarlatamab based on updated data (Global).
- Update the Schedule of Activities to ensure assessment timing and collection is performed as intended to achieve the goals of the study.
- Update the eligibility criteria for stricter guidance on hepatitis B and C exclusion criteria.
- Update the eligibility criteria on brain metastasis exclusion criteria.
- Update the eligibility criteria with clarification on “mixed histology” exclusion criteria.
- Update in the recommendation guidelines for the management of cytokine release syndrome (CRS) to include the consideration for administration of dexamethasone in grade 1 and 2 CRS.
- Update dose modification guidelines for ICANS and related neurological events and seizures in alignment with Immune Effector Cell Toxicity Assessment and Management (also known as CARTOX) guidelines.
- Remove language that disease progression of SCLC and death due to disease progression are not considered and reported as adverse events or serious adverse events as this does not apply to studies that are ongoing.
- Update the language in Regulatory Reporting Requirements for Safety Information to incorporate language in alignment across Amgen protocols.
- Make other administrative, typographical, abbreviation, and formatting changes throughout the protocol for consistency and clarification as needed.

Protocol Amendment 2**06 September 2023**

The study was updated based on the latest data obtained from the Phase 2 Study to

- Include a reduction in monitoring to [REDACTED] hours after cycle 1 day 1 (C1D1) and cycle 1 day 8 (C1D8).
- Remove the requirement for evaluable tumor as an inclusion criterion, based on analysis of the relationship between delta-like ligand 3 (DLL3) expression and the efficacy seen.
- Reduce the sample size.

The protocol was amended to:

- Remove the requirement of pre-screening period and tissue biopsy with an allcomers strategy.
- Update the number of subjects to [REDACTED] subjects, approximate number of sites to 240, and total study duration to approximately 4 years.
- Remove the requirement for hospitalization post-infusion and replace with reduced monitoring guidance.
- Update the topotecan (China) intravenous dose to 1.2 mg/m² or other locally approved dose.
- Update the schedule of activities table:
 - to remove pre-screening (archival tumor tissue/biopsy), C-reactive protein, ferritin, and endocrine panel
 - to add demographics information, prior therapies review, thyroid stimulating hormone, free T4 assessments, and tumor tissue collection assessments
 - to update physical examination to inform that weight must be collected at each day 1, vital signs and pulse oximetry, and pharmacokinetic and anti-tarlatamab antibody collection windows
 - to update urinalysis, 12-lead electrocardiogram (ECG), hematology, and chemistry panel assessments.
- Remove exploratory objectives and endpoints.
- Update the inclusion/exclusion criteria:
 - to include subjects with histologically or cytologically confirmed small cell lung cancer (SCLC) with demonstrated progression or relapse
 - to include subjects with prothrombin time (PT)/international normalized ratio (INR) and partial thromboplastin time (PTT) or activated partial thromboplastin time (APTT) ≤1.5 x institutional upper limit of normal (ULN) except for subjects undergoing oral anticoagulation using vitamin K antagonists
 - to clarify that subjects must be on a stable dose of anticoagulant therapy for 2 weeks prior to enrollment
 - to exclude subjects with prior therapy with tarlatamab or any of the standard of care (SOC) chemotherapy included as part of this trial or in any tarlatamab clinical trial.
- Update that product lot number will be recorded at the site level for SOC chemotherapy.

- Update the supply information for topotecan Accord and Hydrochloride (AoLuoNa) injection.
- Add a reference to the regional prescribing information or institutional guidelines for additional information regarding rescue medication.
- Rephrase “dose change” and replace with tarlatamab and SOC chemotherapy “delay or discontinuation”.
- Update the tarlatamab and dose modification guidelines for adverse events.
- Update the details regarding vital signs and pulse oximetry.
- Add that whole blood samples will be collected for immunophenotyping by flow cytometry in approximately 200 subjects (100 patients per arm) to identify changes in peripheral immune cell subsets and activation status.
- Clarify that further details of the censoring rules will be described in the statistical analysis plan (SAP).
- Remove details regarding progression-free survival (PFS) Censoring Rule.
- Add that the local laboratory may report granulocytes instead of neutrophils, eosinophils, and basophils individually.
- Remove the Cairo Bishop grading of tumor lysis syndrome.
- Align protocol-required therapy language with language from the latest clinical protocol template.
- Update the National Clinical number of the study.

Protocol Amendment 1

30 May 2023

Protocol amendment 1 was made mainly to address feedback received from the regulatory agency. Changes driven by regulatory feedback are listed below.

- Provided additional language to clarify the purpose for having an optional pre-screening phase in the study. This pre-screening phase allows for an early assessment of tumor biopsy, early identification of eligible subjects, and consequently a reduction in the time between the last cycle of first-line therapy and the first treatment within the study.
- Specified that serum pregnancy test at screening must be performed within 7 days of cycle 1 day 1 and all additional pregnancy tests (serum or urine) must be performed at day 1 of each cycle and reviewed before treatment administration.
- Updated eligibility criteria for patients who have progressed or recurred following 1 platinum-based regimen to add that only patients who per investigator discretion are candidates for the 3 standard of care therapies should be included.
- Added that after completion of tarlatamab treatment, live and live-attenuated vaccines are prohibited for 42 days after last dose of tarlatamab.
- Updated tarlatamab dose modification guidelines for adverse events to:
 - Add specific guidelines for administration of corticosteroids by specifying dosing of corticosteroids (8 mg to 16 mg of dexamethasone or equivalent) and frequency of administration (every 8 hours) to manage neurologic events.
 - Clarify that for neurological events grade 4, tarlatamab administration must be permanently discontinued rather than interrupted/delayed.
- Other administrative changes were included in this protocol amendment which represented general corrections or clarifications. These changes are listed below.
 - Informed in the protocol that the clinical study will be published within 1 year of completion on clinicaltrialsregister.eu.
 - Clarified that subjects in China randomized to standard of care therapy will receive topotecan at a lower intravenous dose.
 - Updated Schedule of Activities tables for adverse events, serious adverse events, and concomitant therapy to correctly show timing on which of these assessments are to be completed.
 - Updated Schedule of Activities tables for vital signs, pulse oximetry assessment to clarify collection time.
 - [REDACTED]
 - Updated hospitalization and monitoring guidance for cycle 2 from “8 hours” to “6 to 8 hours” to maintain consistency across cycle 1 and cycle 2 observation hours.
 - Aligned collection and reporting of safety events with current procedures.
 - Corrected administrative errors in the Schedule of Activities tables to ensure alignment between tables and footnote details.
 - Corrected minor errors related to description of planned analyses.
- Incorporated administrative and editorial changes (including document version date, grammatical, typographical, abbreviations, and formatting) throughout the protocol.

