6.1.2 Noninvestigational/Auxiliary Medicinal Products

In some regions, the investigational product(s) and/or noninvestigational product(s)/auxiliary medicinal product(s) described in Section [6.1.1.1](#) and administered for preventative, diagnostic, or therapeutic reasons, may be considered noninvestigational medicinal products.

All other noninvestigational product(s)/auxiliary medicinal product(s) including, tarlatamab pre- and post-infusion medication (dexamethasone and IV hydration) and standard of care (SOC) chemotherapy co-medications, that are commercially available are not provided by Amgen (except if required by local regulation). The investigator will be responsible for obtaining supplies of these noninvestigational product(s)/auxiliary medicinal product(s).

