4 (cont)			
If tocilizumab is not available, siltuximab (an anti-IL-6 monoclonal antibody) may be used in the management of CRS, following the criteria outlined in this table. The recommended dose of siltuximab is 11 mg/kg administered over 1 hour as an IV infusion, consistent with the prescribing information for the treatment of multicentric Castleman's disease (Sylvant Prescribing Information), and the CARTOX Working Group Guidelines for CRS management (Neelapu et al, 2018). Siltuximab may be repeated if needed, in the event that CRS recurs after a subsequent infusion of tarlatamab. Siltuximab may not be repeated in an individual subject who develops anaphylaxis to siltuximab, or gastrointestinal perforation after siltuximab. 
Monitor:
 
CRS symptoms including temperature, blood pressure, and pulse oximetryFluid status, maintain IVF as neededConsider chest X-ray and obtaining appropriate cultures to rule out infectionIf refractory hypotension (after 2 fluid boluses), consider ECHO 
Admit to intensive care unit for close clinical and vital sign monitoring per institutional guidelines.
		

Abbreviations and footnotes defined on last page of table.

Table 6-2. Tarlatamab Dose Modification Guidelines for Adverse Events

Grade	Interruption/Delay	Specific Management	Restart guidance	Permanent Discontinuation
Tumor Lysis Syndrome (TLS) – Grading according to Common Terminology Criteria for Adverse Events (CTCAE v5.0) (see Section 11.11.3)				
Present	Immediate interruption/delay until event has improved to grade ≤ 1	
TLS should be managed according to the local SOC and institutional guidelines.
 
• Resume only if successfully managed and improvement to \leq grade 1 in ≤ 14 days• Consult with Amgen medical monitor.• In case of infusion interruption, continue treatment with next schedule infusion, do not resume prior infusion or administer delayed infusion.• Monitoring: per Monitoring Guidance for first tarlatamab administration (Section 6.1.1)	
If subject missed more than 2 consecutive doses of tarlatamab
 
OR
 
In case of repeat TLS event, or life-threatening TLS, permanently discontinue tarlatamab.
	

Abbreviations and footnotes defined on last page of table.

Table 6-2. Tarlatamab Dose Modification Guidelines for Adverse Events

Grade	Interruption/Delay	Specific Management	Restart guidance	Permanent Discontinuation

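### The laboratory TLS window in Protocol Section 11.11.3 closes on C1D8, the day of the first 10 mg dose, so the Table 6-2 TLS hold and repeat-event stop do not literally reach TLS after target doses

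*Protocol*

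**What the plan says.** Protocol Section 11.11.3 makes the Cairo-Bishop system the test of whether TLS exists in this trial: the "classification will be used to define presence of TLS, ie, presence of laboratory TLS" and clinical TLS. Clinical TLS itself requires laboratory TLS plus a complication, so without laboratory TLS there is no TLS of either kind. CTCAE version 5.0 then sets the grade, and the section lists only grades 3, 4 and 5.

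The time window is stated twice. The body text reads "laboratory TLS is defined as any 2 or more abnormal serum values present within 3 days before or 7 days after initiation of treatment". That sentence goes on to attach two conditions, adequate hydration and a hypouricemic agent. In the note under Table 11-8, "Two or more laboratory changes within 3 days before or 7 days after cytotoxic therapy will constitute laboratory tumor lysis syndrome", with no hydration or hypouricemic condition.

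The TLS row of Table 6-2 (Section 6.2.2.1) refers to Section 11.11.3. When TLS is present it requires "Immediate interruption/delay until event has improved to grade" 1 or lower, and allows resumption only if that is reached within 14 days. It adds: "In case of repeat TLS event, or life-threatening TLS, permanently discontinue tarlatamab". More than 2 consecutive missed doses also ends treatment.

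Table 6-1 gives 1 mg on C1D1, 10 mg on C1D8 and C1D15, and 10 mg every 2 weeks after that.

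**The concern.** A window counted from the start of treatment would suit a drug given at full dose from day 1. Here the first dose is a deliberately small step dose, and exposure at the target dose begins only when the window is closing. Section 2.3 names TLS as a potential safety concern of tarlatamab, so one would expect the rule to cover the doses that carry most of the exposure.

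The row's other provisions suggest that it was meant to. A stop for a repeat event presupposes a hold, a recovery, a restart and a second event. A limit on consecutive missed doses presupposes that dosing is under way. Uric acid is listed in Table 11-1 through cycle 2, well past C1D8.

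What is at stake is consistency of dosing decisions across about 240 sites. Suppose a C1D15 pre-dose panel shows potassium and phosphorus both above the Table 11-8 limits. A site that follows the body text records no TLS and uses its own judgment about the dose. A site that reads the note as applying to each administration records TLS, holds the dose, and stops tarlatamab if this is a second event.

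**Working it through.** The plan states no derived figure here, so the check is calendar arithmetic, with C1D1 as day 1.

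**Inputs**
- Doses in cycles 1 and 2 (Table 6-1; 28-day cycles): day 1 (1 mg); days 8, 15, 29 and 43 (10 mg).
- Cycle 1 visit window: ±1 day (Table 1-1, footnote b).
- C1D8 and C1D15 local laboratory tests: up to 48 hours before the dose (Table 1-1, footnote d).
- Dosing-day procedures precede the dose unless otherwise noted (Table 1-1, footnote a).

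**Closing day under the body text**
- Day 1 + 7 = day 8 = C1D8.
- If the first 10 mg dose is given on day 7, 8 or 9, the window still holds 2, 1 or 0 calendar days on or after that dose, counting the dosing day.
- The scheduled C1D8 pre-dose panel reflects only the 1 mg dose.

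**Follow-up after the 10 mg doses**
- Days 1 to 7 after each dose: 9–15, 16–22, 30–36 and 44–50, which is 4 × 7 = 28 distinct days.
- Overlap with a window ending on day 8: 0 of 28. If the first 10 mg dose is on day 7, its follow-up is days 8–14 and the overlap is 1 of 28.
- The step dose is covered for 7 of 7 days (days 2–8).

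**The C1D15 pre-dose sample**
- Visit on day 14 to 16, less 0 to 2 days: sample on day 12 to 16.
- Time since initiation: 12 − 1 = 11 to 16 − 1 = 15 days, always beyond 7.
- Time since the first 10 mg dose: nominally day 13 to 15 less day 8, which is 5 to 7 days. With visit windows on both doses, 12 − 9 = 3 to 16 − 7 = 9 days.

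**The repeat-event stop**
Under the body text, a first event, a hold, a recovery, a restart and a second event would all have to fall by day 8, while the second planned dose is itself on day 8. The only escape is to treat a repeated step dose (Table 6-3) as a new initiation, and the protocol does not say that it is.

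**Calendar coverage of the first 56 days**
- Body text: days 1–8 = 8 days.
- From 3 days before the first dose, and 7 days after any dose: days 1–22, 29–36 and 43–50 = 22 + 8 + 8 = 38 days.
- From 3 days before to 7 days after every dose: days 1–22, 26–36 and 40–50 = 22 + 11 + 11 = 44 days.

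These count calendar days. They are not counts of samples or subjects.

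**The case against.** A reader might infer that the section contains two flatly conflicting anchors, one for the start of treatment and one for each dose. The documents do not support that. The note never mentions each dose. It gives the same 3-day and 7-day limits for the same definition and may be shorthand for the body text. It may also not concern tarlatamab: Section 2.1 calls lurbinectedin cytotoxic and describes tarlatamab as a T cell engager, and Table 6-2 applies only to tarlatamab. This objection stands against a claim of contradiction but does not remove the gap. On either of those readings, the only window that reaches the tarlatamab row still ends on C1D8.

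A reader might also infer that subjects would be dosed through TLS. That goes too far. Table 6-2 is headed as guidelines, Section 6.2.2.1 provides for delay or discontinuation when the investigator judges that toxicity warrants it, and results must be reviewed before dosing. A clinician who sees two grossly abnormal values is unlikely to dose under any reading. These safeguards are real. They leave the outcome to judgment where the row was written to fix it.

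A third inference is that the hypouricemic clause makes laboratory TLS impossible, because the tarlatamab pre- and post-infusion medications are dexamethasone and IV hydration only (Section 6.1.2). The clause more plausibly describes the setting of the cited classification. It is worth one clarifying sentence and is not evidence that the rule fails outright.

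Finally, a window running from 3 days before every dose, with no clinical qualifier, would label more electrolyte abnormalities from other causes as TLS, and a second such label forces a permanent stop. That is a fair objection to a broad remedy, and the change proposed here is narrower for that reason.

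**Conclusion.** The point holds as a defect in a stated safety rule. Followed literally, Section 11.11.3 does not recognise TLS in the 7 days after any 10 mg dose, apart from what remains of C1D8 itself (or of days 7 and 8 if the dose is a day early). The Table 6-2 hold is then discretionary after target doses, and the repeat-event stop has almost nothing to act on.

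The practical effect is small. The documents give no TLS rate; that few subjects would be affected is a judgment. The SAP provided, which covers integrated safety, does not list TLS among its events of interest (Section 5.4.4.2). The effect is therefore on dosing decisions and on TLS reported as an adverse event, and the overall survival analysis is not affected.

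The conclusion assumes that initiation of treatment means C1D1 and that a repeated step dose is not a new initiation. If it were one, the window would reopen for those subjects only. The change is worth making because it corrects the rule at little cost.

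**What to change.** 1. Use one wording in the body text of Section 11.11.3 and in the note under Table 11-8: *from 3 days before the first dose, and within 7 days after any dose of study treatment (for tarlatamab, the step dose, each target dose and any repeated step dose), and not explained by another cause*. Referring to study treatment keeps a definition for the standard of care arm.
2. State that use of a hypouricemic agent is not required for laboratory TLS.
3. In the TLS row of Table 6-2, replace grade 1 or lower with *TLS resolved*, because the section lists no CTCAE grade below 3 for TLS. Keep the 14-day limit for resumption.

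This edits one definition, one table note and one table row, with no new visits or samples and no change to sample size or alpha. The costs are a few more holds, possibly a rare additional permanent stop, and slightly different ascertainment of TLS before and after the amendment. After cycle 2 uric acid is no longer listed, so the definition then rests on potassium, phosphorus and calcium; two abnormal values can still be met.

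One limit remains. At nominal 2-week spacing, a pre-dose sample is 12 to 14 days after the previous dose (14 less 0 to 2) and stays outside the window. Values at that point would still be handled by pre-dose review and investigator judgment.
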